### 3.1.3 Additional Research Program

To understand the mechanisms of illness and recovery and how AT-II affects them, further biomarkers will be measured (e.g. KIM-1, NGAL, renin, HA and anti- and proinflammatory mediators (IL-6, IL-10...)). Blood and urine samples from recruited patients will be collected 4h after CPB, 12h, and 24h after start of intervention. The details of the additional research program will be contained in a separate plan, which will be finalized before the final analysis.

## 3.2 Endpoints

### 3.2.1 Primary Endpoint

The primary study endpoint is

- **Difference between [TIMP-2]\*[IGFBP7] levels 12h after randomization and [TIMP-2]\*[IGFBP7] levels at randomization.**

### 3.2.2 Secondary Endpoints

- occurrence of AKI within 72h after cardiac surgery (according to the KDIGO criteria)
- occurrence of moderate and severe AKI within 72h after cardiac surgery (according to the KDIGO stage 2 and 3)
- amount of volume application within 12h after randomization
- fluid status 12h after randomization
- dose of vasopressor use during intervention
- creatinine clearance on day one after cardiac surgery
- free-days through day 28 of vasoactive medications and mechanical ventilation
- renal recovery at day 90 (renal recovery is defined as serum creatinine levels  $< 0.5$  mg/dl higher than baseline serum creatinine (creatinine level before surgery)
- 30-day, 60-day and 90-day mortality
- length of ICU stay
- length of hospital stay
- use and duration of renal replacement therapy within hospital stay
- use of RRT at days 30, 60, 90
- MAKE90 (major adverse kidney events consisting of mortality, dialysis dependency, persistent renal dysfunction (defined as serum creatinine  $\geq 2x$  compared to baseline value) at day 90
- Effect of ACEi/ARBs use on the AT II effect
- Correlation between the severity of hyperreninemia and the AT II effect

Other variables:

- Surveillance of vital parameters on ICU
- Safety laboratory parameters
- Occurrence of thromboembolism
- Adverse events

Add-on study:

- determination of further biomarkers (e.g. KIM-1, chitinase, NGAL, renin, hyaluronic acid and anti- and pro-inflammatory cytokine levels (IL-6, IL-10...), leukocyte functions

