### 5.2.3 Distribution of Gender in the Study Population

We expect a gender distribution of (male: female) 70:30. No patient will be excluded from the study on the basis of gender. Gender will be used for covariate adjustment in the final analysis. A subgroup analysis will be performed according to gender.

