### 9.2 Intermediate Visits

#### T2 Baseline (during surgery until 4 h after terminating CPB)

- Nature of surgical procedure
- Time of skin incision, time of skin suture
- Duration of CPB
- Duration of aortic cross clamp
- Fluid input and output
- Hemodynamics (MAP, HR, CVP)
- Concomitant Medication / Pressors

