#### Secondary endpoints

Statistical analysis of the pre-specified secondary endpoints will be performed with descriptive and inferential statistical methods. Secondary outcomes will be evaluated and compared between the randomized treatment arms using the following methods. In case of normally or non-normally distributed metric outcomes, Student's t test or the Mann-Whitney U test will be applied, respectively. Categorical outcomes will be analyzed using Fisher's exact test (2x2 tables) or the Chi test (>2x2 tables). Survival data will be analyzed using the Kaplan-Meier method and the log-rank test. Hazard ratios will be estimated based on Cox proportional hazards models after checking the proportional hazards assumption based on the Schoenfeld residuals.

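### Fluid status at 12 h and vasopressor dose are compared without the pre-randomisation values that the protocol records; the comparison stays unbiased but loses precision

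*Protocol*

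**What the plan says.** Three secondary endpoints in Section 3.2.2 concern fluids and vasopressors: "amount of volume application within 12h after randomization", "fluid status 12h after randomization" and "dose of vasopressor use during intervention". The first and third cover a period that begins at or after randomisation. The second names a time point, and no start of the balance is given. The synopsis lists fluid status with no time at all.

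For metric outcomes, the secondary-endpoint paragraph of Section 12 says that, for normal or non-normal data, "Student's t test or the Mann-Whitney U test will be applied, respectively". The multivariable paragraph of Section 12 describes Cox and logistic models for finding prognostic factors and gives no model for metric outcomes. The only adjustment covariate named is in Section 5.2.3: "Gender will be used for covariate adjustment in the final analysis".

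Section 9.2 lists "Fluid input and output" and "Concomitant Medication / Pressors" at T2, which runs from surgery to 4 h after bypass and so ends before randomisation. The flow chart, as it reads, ticks pressors and fluid balance only from T3 onwards.

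**The concern.** These two endpoints lie close to the haemodynamic action of the drug. A patient's vasopressor need at randomisation plausibly predicts the dose over the next 12 h. Entry requires hypotension needing a vasopressor but sets no dose range, so starting needs may vary widely. Balance carried over from surgery may likewise relate to fluid status at 12 h.

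With about 30 evaluable patients per arm, variation that a recorded starting value could explain stays in the error term and widens the interval. A chance difference between arms in that starting value also carries through to the contrast. The choice of test is written in the protocol, so this is a stated choice and not a detail left to a statistical analysis plan.

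**Working it through.** **Inputs from the protocol (Section 12 unless stated).** 32 randomised and 30 evaluable per arm, 5% dropout, two-sided alpha 0.05; 1:1 allocation (Section 6).

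**The plan's own figure.** 30 / 0.95 = 31.6, rounded up to 32 per arm. This reproduces. No precision or power is stated for the two secondary endpoints.

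**Assumption.** The protocol gives no correlation *r* between pre-randomisation value and outcome, so a range is shown.

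**Unadjusted comparison.** The 95% half-width is t(0.975, 58) × √(2/30) = 0.517 outcome SD. By normal approximation, power for a true difference of 0.5 SD is 49%.

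**Adjusted comparison.** The variance is multiplied by (1 − r²) and the half-width by √(1 − r²).

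| r | variance factor | half-width (SD) | narrower by | power at 0.5 SD |
|---|---|---|---|---|
| 0.2 | 0.96 | 0.507 | 2% | 51% |
| 0.3 | 0.91 | 0.493 | 5% | 53% |
| 0.5 | 0.75 | 0.448 | 13% | 61% |
| 0.7 | 0.51 | 0.369 | 29% | 77% |

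Estimating the slope costs a variance factor of about 1 + 1/56 = 1.018. At r = 0.2 the net variance factor is 0.96 × 1.018 = 0.977, a half-width about 1% narrower, which is almost nothing. At r = 0.5 the gain equals having 30 / 0.75 = 40 patients per arm; at r = 0.7, 30 / 0.51, or about 59.

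**Chance imbalance.** The difference in starting means has SD √(2/30) = 0.258 of the starting-value SD. The chance that it exceeds 0.25 SD in either direction is 33%, and 0.5 SD, 5%. An imbalance of 0.5 SD moves the unadjusted contrast by 0.5 × r outcome SD, or 0.25 SD at r = 0.5.

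**Fluid status as a cumulative level.** Let B be the balance before randomisation and D the balance accrued after it. The level is B + D. If B and D are independent, the unadjusted standard error for the level exceeds that for D by √(1 + var(B)/var(D)): 1.22, 1.41 or 1.73 for variance ratios of 0.5, 1 or 2. These ratios and the independence are assumptions. With correlation −0.5, SD(D) = 1.0 L and SD(B) = 0.5 L, the level has SD √(1 + 0.25 − 0.5) = 0.87 L, below the 1.0 L of D. The sign of the loss from using the level therefore depends on the correlation.

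A model with arm and B removes this dependence. Given B, the residual SD is √(1 − 0.25) × 1.0 = 0.87 L for the level and for D alike, because the two differ only by B. On the untransformed scale the adjusted arm contrast is the same for both.

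**The case against.** The strongest reply is that nothing here is invalid. Randomisation makes the unadjusted test sound, and its error rate and interval already allow for chance imbalance. These are two of many secondary endpoints in what Section 4 calls a feasibility trial, and no primary conclusion rests on them. That stands, and it limits the point to efficiency.

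A reader might infer that doses given before treatment contaminate the dose endpoint. They do not: the endpoint covers only the intervention period, so earlier need is at most a predictor. It may be a weaker one in the AT-II arm, where norepinephrine is to be weaned.

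A reader might also infer that fluid status necessarily contains the balance from surgery and bypass. Setting a time point beside a 12 h window makes that reading possible, but the protocol never defines the term. If the balance starts at randomisation, no earlier litres enter.

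Unequal slopes in the two arms, or a negative correlation between earlier and later balance, do not defeat adjustment. With 1:1 allocation, a model with arm plus starting value is, in large samples, no less precise than the unadjusted comparison; robust standard errors deal with unequal slopes.

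One practical objection also stands. A vasopressor rate at randomisation is not a defined data item. T2 ends 4 h after bypass, randomisation follows the renin result, and the flow chart disagrees with Section 9.2.

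**Conclusion.** The point holds as a loss of precision in two secondary endpoints. The protocol fixes unadjusted tests while listing the relevant pre-randomisation data for collection. Adjustment would narrow the intervals by about 5% to 29% for correlations of 0.3 to 0.7, and by almost nothing at about 0.2 or below. These correlations are assumed, and the protocol cannot settle which applies.

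The separate problem for fluid status, that pre-treatment balance is part of the endpoint, is conditional on a cumulative reading that the text permits but does not state. The documents do not support a claim of bias, nor any fixed size of loss.

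**What to change.** 1. **Section 3.2.2:** state that the fluid balance behind fluid status starts at randomisation.
2. **Section 12:** compare fluid status and vasopressor dose by a model with arm plus the pre-randomisation value: T2 fluid balance for the first, the last recorded vasopressor rate before randomisation for the second. Use ranks or logs if the data are skewed, with robust standard errors. Keep the t test or Mann-Whitney test as a sensitivity analysis.
3. **Flow chart:** align it with Section 9.2, so that pressors and fluid balance are shown before T3, and make sure that the vasopressor rate is recorded with its time.

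The cost is a few sentences, one degree of freedom and a slightly more complex analysis. No new visit is needed, and Section 9.2 already lists the underlying data; only the rate and its time need to be specified as an item.

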## 4 Study Design

The Aided-trial is a single center, prospective, interventional, phase IIIa, two-arm parallel group, randomized-controlled, double blinded trial including 64 patients at high risk for the development of AKI after cardiac surgery with CPB.

### Discussion of trial design

To the best of our knowledge, no trial has been performed investigating the effect of AT-II on kidney damage in patients at high risk for AKI undergoing cardiac surgery. Our preliminary data demonstrate that elevated renin levels were associated with cardiovascular instability and increased rates of AKI after cardiac surgery. In order to investigate whether AT-II can also prevent kidney damage in high-risk patients undergoing cardiac surgery, we will perform a feasibility trial. If we can demonstrate that AT-II mitigates kidney damage in high-risk patients undergoing cardiac surgery, a follow-up trial could investigate whether AT-II can significantly reduce the occurrence of AKI after cardiac surgery. Therefore, this study is necessary to demonstrate that biomarker-guided implementation of AT-II can mitigate kidney damage after cardiac surgery. If the trial is positive, we will use the data and study protocol to apply for an interventional trial showing that renin-level-guided AT-II application reduces kidney damage after cardiac surgery.

## 5 Study Sites and Study Population

### 5.1 Study Site Selection

The study will be performed as a single-center randomized-controlled trial. The Department of Anesthesiology, Intensive Care and Pain Medicine at the University Hospital of Muenster has a lot of experience with randomized-controlled trials. The study team consists of experienced investigators and study nurses. The measurement of [TIMP-2]\*IGFBP7 will be performed with the NephroCheck® test (Astute, San Diego, CA, USA) which is available at the corresponding cardiac surgical ICU. The IMP will be prepared and the applied through independent personnel to ensure blinding of the process.

### 5.2 Study Population

Patients at high risk for AKI after cardiac surgery with CPB will be identified by hyperreninemia ( $\Delta$ -renin (difference between post- and pre-operation)  $\geq 3.7 \mu\text{U/ml}$  4 h after CPB).

#### 5.2.1 Inclusion Criteria

##### Inclusion criteria for registration

1. Adult patients undergoing cardiac surgery with CPB
2. 18 years of age or older
3. Cardiac index  $> 2.1 \text{ l/min per square meter}$
4. Written informed consent

##### Inclusion criteria for randomization

Registered patients will be randomized only if

1.  $\Delta$ -renin (difference between post- and pre-operation)  $\geq 3.7 \mu\text{U/ml}$  4 h after CPB
2. Postoperative hypotension requiring vasopressors

#### 5.2.2 Exclusion Criteria

1. Preexisting AKI (stage 1 and higher)

2. Patients with cardiac assist devices (ECMO, LVAD, RVAD, IABP)
3. Pregnant women, nursing women and women of childbearing potential
4. Known (Glomerulo-) Nephritis, interstitial nephritis or vasculitis
5. CKD with eGFR < 30 ml/min
6. Dialysis dependent CKD
7. Prior kidney transplant within the last 12 months
8. Emergency surgery in the context of an acute coronary syndrome
9. Hypersensitivity to the active substance, or to any of the excipients of the study medication
10. Bronchospasm
11. Liver failure
12. Mesenteric ischemia
13. Participation in another intervention trial in the past 3 months
14. Persons with any kind of dependency on the investigator or employed by the institution responsible or investigator
15. Persons held in an institution by legal or official order

### 5.2.3 Distribution of Gender in the Study Population

We expect a gender distribution of (male: female) 70:30. No patient will be excluded from the study on the basis of gender. Gender will be used for covariate adjustment in the final analysis. A subgroup analysis will be performed according to gender.

## 6 Patient Inclusion, Registration and Randomization

Patients who are cared for at the study sites and who are possibly eligible will be invited for study participation until the desired number of patients is achieved. Once written informed consent for participation has been given (cf. section 15.215.2), a subject identification code will be assigned.

After successful registration, when patients meet all designated inclusion criteria (including identifying a high risk patient ( $\Delta$ -renin (difference between post- and pre-operation)  $\geq 3.7 \mu\text{U/ml}$  4 h after CPB), and none of the exclusion criteria, patients will be randomized using an internet-based randomization tool at <https://www.randomizer.at>. Randomization will be performed in a proportion of 1:1.

The time interval between patient fulfilling eligibility criteria and start of infusion may not exceed 30 minutes.

## 7 Study Medication

### 7.1 Investigational Medicinal Product:

The trial sites will use the study medication as article of trade, which will be used routinely in the hospital.

Patients randomized to the intervention group will receive AT-II (10,000ng/ml Giapreza®) for 12 h after randomization. The starting dose will be 20 ng/kg/min and the dose will be adjusted (up to 80 ng/kg/min) so that the other vasopressors can completely weaned and the mean arterial pressure is  $> 65 \text{ mmHg}$ . Patients randomized to the control group will receive placebo (0.9 % NaCl).

#### 7.1.1 Drug Characterization

##### 7.1.1.1 Name of the medicinal product

Giapreza®, concentrate for solution for infusion

Control/Placebo: Isotone Natriumchloridlösung 0,9 % Braun  
Infusionslösung.

#### 7.1.1.2 Qualitative and quantitative composition

##### **Giapreza®**

1 ml contains:

##### **Active substance Quantity**

Angiotensin-II-Acetat 2.5mg

osmolarity: 130 to 170 mOsmol/kg

pH value: 5.0 - 6.0

##### **Control/Placebo:**

100 ml contains: Natrium chloride: 0,9 g

Electrolyte concentrations:  $\text{Na}^+$ : 154 mmol/l,  $\text{Cl}^-$ : 154 mmol/l

Theoretical osmolarity: 308 mosmol/l

Titration acidity (pH 7,4): < 0,3mmol/l

#### 7.1.1.3 List of excipients

##### **Giapreza®:**

Excipients: Mannitol, Water for injections, Sodium hydroxide (for pH adjustment),

Hydrochloric acid (for pH adjustments)

##### **Control/Placebo:**

Water for injections

#### 7.1.1.4 Pharmacodynamic properties

##### **Giapreza®**

Angiotensin II (AT II) increases blood pressure by vasoconstriction; the increased release of aldosterone by direct action of AT-II on the vessel wall is mediated by binding to the G-protein-coupled AT-II receptor type 1 on vascular smooth muscle cells, stimulating  $\text{Ca}^{2+}$ /calmodulin-dependent phosphorylation of myosin and causing smooth muscle contraction.

GIAPREZA is titrated for each individual patient by effect. In the ATHOS-3 study, the median time to increase in blood pressure was approximately 5 minutes. The effect on blood pressure is sustained for at least the first three hours of continuous intravenous infusion. Because of the short half-life of GIAPREZA (less than one minute), abrupt discontinuation of AT may result in rebound hypotension.

Therefore, after sufficient improvement of the underlying shock, slow down-titration in increments of up to 15 ng/kg per minute, as controlled by blood pressure values, is recommended as needed.

##### **Control/Placebo:**

Sodium is the major cation of the extracellular fluid space and regulates its size along with various anions. Sodium and potassium are the main carriers of bioelectrical processes in the organism.

The sodium content and fluid metabolism of the organism are closely linked. Any change in plasma sodium concentration that deviates from the physiological level simultaneously influences the fluid status of the organism. Regardless of the serum osmolality, an increased sodium content means an increased fluid content or a reduced sodium content of the organism a decrease in body water.

A 0.9% sodium chloride solution corresponds to plasma osmolarity. Upon delivery of this solution, it comes first to replenish the interstitium, which makes up about 2/3 of the

extracellular space. Only about 1/3 of the volume delivered remains intravasal. The solution is thus hemodynamically effective only for a short time.

#### 7.1.1.5 Pharmacokinetic properties

##### **Giapreza®**

No specific studies have been conducted to investigate the metabolism and excretion of GIAPREZA. The half-life of intravenously administered AT-II in plasma is less than one minute. It is metabolized by end cleavage (at both the amino and carboxy terminals) in various tissues, including erythrocytes, plasma, and major organs (e.g., intestines, kidneys, liver, and lungs). No trials have been conducted to investigate the pharmacogenetics of AT-II in renally impaired patients and/or in patients with hepatic impairment since the kidneys and the liver are not a major organ for AT-II metabolism or excretion.

#### 7.1.1.6 Shelf-life

##### **Giapreza®**

3 years.

To be used immediately after the bottle is opened.

Giapreza® is not to be stored after addition of other components.

##### **Control/Placebo:**

3 years.

To be used immediately after the bottle is opened.

For microbiological reasons, the ready-to-use preparations should be used immediately. Normally, blends with other components should not be stored for more than 24 hours at 2°C – 8°C unless they have been prepared under controlled and validated aseptic conditions

#### 7.1.1.7 Special precautions for storage

##### **Giapreza®**

Store in a refrigerator ( 2-8°C). For storage conditions after dilution of the medicinal product see 7.1.1.6.

##### **Control/Placebo:**

This medicinal product does not require special storage conditions.

#### 7.1.1.8 Marketing authorization holder

**Giapreza®:** PAION AG, Aachen, Deutschland

**Control/Placebo:** B. Braun Melsungen AG, Melsungen, Deutschland

#### 7.1.1.9 Marketing authorization numbers

**Giapreza®:** EU/1/19/1384/001; EU/1/19/1384/002; EU/1/19/1384/003

**Control/Placebo** (Isotone Natriumchloridlösung 0,9% Braun): 6697366.00.00; 6726174.00.00

## **7.1.2 Contraindications**

**Giapreza®:** Hypersensitivity to the active substance or to any of the excipients listed in 7.1.1.2

##### **Control/Placebo:**

None

### 7.1.3 Special Warnings and precautions for use

#### Giapreza®

The clinical experience with GIAPREZA is limited to septic or other distributive shock. The use of GIAPREZA is not recommended in other types of shock (e.g. cardiogenic shock, etc aspatients with non-distributive shocks were excluded from clinical trials.

Thromboembolic events have reported with the use of angiotensin II in clinical trials. The major imbalance compared to placebo was in venous thromboembolism (6.1% vs 0%). Concurrent venous thromboembolism prophylaxis should be used unless contraindicated during treatment with GIAPREZA. Non-pharmacologic venous thromboembolism prophylaxis may be considered where pharmacologic prophylaxis is contraindicated.

Peripheral ischaemia has been reported with the use of AT-II. It is important to administer GIAPREZA at the lowest compatible dose to achieve or maintain adequate mean arterial pressure and tissue perfusion.

#### Control/Placebo:

Isotonic sodium chloride solution 0,9% should be used with caution in

- Hypernatremia
- hyperchloraemia

### 7.1.4 Interaction with other Medicinal Products and other Forms of Interaction

#### Giapreza®:

No interaction studies have been performed. No invitro metabolism studies have been performed with GIAPREZA.

Concomitant administration of GIAPREZA and other vasopressors may have an additive effect on mean arterial pressure (MAP). The addition of GIAPREZA may require a reduction in doses of other vasopressors.

Patients who have recently received angiotensin converting enzyme (ACE) inhibitors may be more sensitive to GIAPREZA's action with an increased response. Patients who have recently received angiotensin II receptor blockers (ARBs) may be less sensitive to GIAPREZA's actions with a reduced response

#### Control/ Placebo:

No interactions are known to date.

### 7.1.5 Undesirable Effects

Giapreza®: The most frequent adverse reactions ( $\geq 1/10$ ) reported more often are thromboembolic events (12.9% vs 5.1%) and transient hypertension. Common adverse reaction ( $\geq 1/100$  to  $< 1/10$ ) were Tachycardia and peripheral ischaemia.)

Control/Placebo: Side effects are not expected under normal use.

### 7.1.6 Administration

After identifying cardiac surgery patients at high risk for AKI by renin levels, patients will be randomly allocated to the control or intervention group.

#### Giapreza®

Solution for infusion after mixture with a compatible infusion solution should be infused via the

central venous route.

#### Daily dose

Giapreza will be added to the first-line vasopressor (norepinephrine) and the dose will be adjusted so that the mean arterial pressure is above 65 mm Hg and first-line vasopressor can be weaned to a low level. The recommended starting dosage of GIAPREZA is 20 nanograms (ng)/kg per minute via continuous intravenous infusion.

GIAPREZA must be diluted in sodium chloride 9 mg/ml (0.9%) solution for injection prior to use. One or two millilitres of GIAPREZA must be diluted in sodium chloride 9 mg/ml (0.9%) solution for injection to achieve a final concentration of 5,000 ng/ml or 10,000 ng/ml.

When initiating GIAPREZA, it is important to closely monitor blood pressure response and adjust dose accordingly.

Once an infusion has been established, the dose may be titrated as frequently as every 5 minutes in steps of up to 15 ng/kg per minute, as needed, depending on the patient's condition and target mean arterial pressure. Approximately one in every four patients experienced transient hypertension with the angiotensin II 20 ng/kg per minute starting dose in clinical trials (see 7.1.5), thus needing dose down-titration. For critically ill patients, the usual target mean arterial pressure is 65 – 75 mmHg. Do not exceed 80 ng/kg per minute during the first 3 hours of treatment. Maintenance doses should not exceed 40 ng/kg per minute. Doses as low as 1.25 ng/kg per minute may be used.

It is important to administer GIAPREZA at the lowest compatible dose to achieve or maintain adequate arterial blood pressure and tissue perfusion (see 7.1.3). The median duration of treatment in clinical trials was 48 hours (range: 3.5 to 168 hours).

In order to minimise the risk of adverse events derived from prolonged vasoconstriction, treatment with GIAPREZA should be withdrawn once underlying shock is sufficiently improved (see 7.1.3 and 7.1.5). Down-titrate by gradual decrements of up to 15 ng/kg per minute, as needed, based on blood pressure, in order to avoid hypotension due to abrupt withdrawal (see 7.1.3).

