# 1 General Information

## 1.1 Synopsis

Title:	Biomarker-guided implementation of angiotensin-II (AT-II) to reduce the occurrence of kidney damage after cardiac surgery
Short Title:	Aided-Trial
Sponsor's Study Code:	WWU20_0016
EudraCT-No.:	2021-003088-87
Sponsor:	Westfälische Wilhelms-Universität Münster
Investigator:	Univ.-[name]. med. [name]
Indication:	Cardiac surgical patients at high risk for AKI
Study Design:	Single-centre clinical Trial Two-arm, randomised, blinded, controlled, parallel-group trial
Investigational Medicinal Product:	Test product: Angiotensin II acetat (Giapreza 2,5 mg/ml) Reference therapy: Placebo (0.9 % NaCl)
Therapy	
After identifying cardiac surgery patients at high risk for AKI by renin levels (<math>\Delta</math>-renin (difference between post- and pre-operation) <math>\geq</math> 3.7 <math>\mu</math>U/ml 4h after CPB) who require vasopressors, patients will be randomly allocated to the control or intervention group.
 
Experimental intervention: Angiotensin II will be added to the first-line vasopressor (norepinephrine) and the angiotensin II dose and norepinephrine will be adjusted so that the mean arterial pressure is above 65 mmHg and the first-line vasopressor (norepinephrine) can completely be weaned..
 
Control intervention: The control substance (0.9% NaCl) will be added to the first-line vasopressor (norepinephrine) and the dose of the control substance and norepinephrine will be adjusted so that the mean arterial pressure is above 65 mmHg.
 
The treatment with study medication will be performed for 12 hours. If the patient requires a vasopressor after the intervention period, the first-line vasopressor (norepinephrine) is administered..

Objectives:	
The primary objective of this trial is to investigate the efficacy of AT-II vs. standard of care on the biomarkers [TIMP-2]*[IGFBP7] in high-risk patients undergoing cardiac surgery.
 
HYPOTHESIS: Superiority of AT-II in cardiac surgery patient with a hyperreninemia and vasopressor use compared to standard of care with respect to kidney damage (personalized approach).

Endpoints:	
Primary Endpoint:
 

• kidney damage after cardiac surgery identified by the difference between [TIMP-2]*[IGFBP7] levels 12h after

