Patients assigned to the control group receive only standard care and may not have a treatment benefit. However, since a renoprotective effect is still unknown, patients participating in the trial have the same risks as not participating in the trial. Patients with vasoplegia receive vasopressors in order to increase the systemic vascular resistance (SVR) and subsequently the mean arterial blood pressure (MAP). This ensures organ perfusion and oxygen delivery. Norepinephrine is currently the first-line treatment to treat vasoplegia induced by different causes. However, other vasopressors are also available which can increase the SVR and MAP. Although the available vasopressors (norepinephrine, vasopressin, angiotensin II) have different mode of actions, they are all used to secure organ perfusion. As both groups (intervention group and control group) have the same MAP target, leaving out norepinephrine and replacing it by another vasopressor is without an increased risk for the patient.

This trial may result in a substantial improvement in the management of patients at risk of AKI with a potential improvement of patients' outcome. A participation in this trial will not influence the therapeutic treatment of patients after cardiac surgery. All patients receive standard treatment according to the current standards.

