#### Control/Placebo

The Placebo will be added to the first-line vasopressor (norepinephrine) and the dose of the control substance will be adjusted so that the mean arterial pressure is above 65 mm Hg.

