### **7.1.7 Dose Selection Rationale**

Patients allocated to the intervention group will receive Giapreza® according to the package leaflet for a time of 12h.

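### The protocol sets two different norepinephrine goals for the angiotensin II arm, and section 7.1 states the 80 ng/kg/min ceiling without the time limit given in section 7.1.6

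*Protocol*

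**What the plan says.** **Norepinephrine goal, angiotensin II arm.** The synopsis (1.1, Therapy) has both drugs adjusted so that MAP stays above 65 mmHg and "the first-line vasopressor (norepinephrine) can completely be weaned". Section 7.1 agrees: "the dose will be adjusted (up to 80 ng/kg/min) so that the other vasopressors can completely weaned". Section 2.2 defends this approach on the ground that both groups share the same MAP target, so that "leaving out norepinephrine and replacing it by another vasopressor is without an increased risk for the patient". Section 7.1.6 (Daily dose) sets a different goal, namely that "the mean arterial pressure is above 65 mm Hg and first-line vasopressor can be weaned to a low level".

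**Control arm.** In the synopsis, "the dose of the control substance and norepinephrine will be adjusted so that the mean arterial pressure is above 65 mmHg". In section 7.1.6 (Control/Placebo), "the dose of the control substance will be adjusted so that the mean arterial pressure is above 65 mm Hg", with no mention of adjusting norepinephrine. Neither text states a weaning goal.

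**Dose ceiling.** Section 7.1 gives up to 80 ng/kg/min for a 12 h infusion. Section 7.1.6 says: "Do not exceed 80 ng/kg per minute during the first 3 hours of treatment. Maintenance doses should not exceed 40 ng/kg per minute". Section 7.1.7 has angiotensin II given "according to the package leaflet for a time of 12h", and section 8.1 refers to section 7.1.6 for the infusions.

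**Blinding.** Section 4 calls the trial double blinded, and section 7.1.10 specifies identical syringes. Section 5.1 has independent personnel prepare and apply the drug; section 8.3 has the investigator or attending physician administer it.

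**The concern.** Stopping norepinephrine and reducing it to an unquantified low dose are different targets. Titration is a bedside instruction, so a later analysis document cannot settle it once patients have been treated. Section 3.2.2 lists vasopressor dose during the intervention as a secondary endpoint, and the weaning goal feeds directly into that measurement.

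The written goals also differ by arm. Staff who do not know the allocation cannot pursue weaning in one arm and a MAP target alone in the other.

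The ceiling is a safety limit. Section 7.1.3 reports peripheral ischaemia and an imbalance in venous thromboembolism (6.1% against 0%), and asks for the lowest compatible dose. Section 7.1.5 reports thromboembolic events in 12.9% against 5.1%. A dose limit for such a drug should read the same wherever it is stated.

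**Working it through.** **Step 1: the titration rules side by side.**

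| Place | Norepinephrine goal | Angiotensin II ceiling |
|---|---|---|
| Synopsis, experimental arm | complete weaning, MAP above 65 mmHg | not stated |
| 7.1 | complete weaning, MAP above 65 mmHg | 80 ng/kg/min, no time limit |
| 7.1.6, Daily dose | weaning to an undefined low level, MAP above 65 mmHg | 80 in the first 3 h, 40 for maintenance |
| Synopsis, control arm | norepinephrine adjusted to MAP above 65 mmHg, no weaning goal | not applicable |
| 7.1.6, Control/Placebo | norepinephrine not mentioned, MAP above 65 mmHg | not applicable |

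**Step 2: does the protocol say which text governs?**

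- *Ceiling: yes, in effect.* Section 7.1.7 points to the package leaflet and section 8.1 points to 7.1.6. Both favour the time-limited cap.
- *Norepinephrine goal: no.* Following section 8.1 to 7.1.6 gives the low-level version, which departs from the synopsis, section 7.1 and the safety argument in section 2.2. No statement gives one of them precedence.

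**Step 3: size of the ceiling discrepancy.** Inputs are the 12 h infusion (synopsis, 7.1), the 80 ng/kg/min of section 7.1, and the 80 and 40 ng/kg/min of section 7.1.6. Maintenance is taken to start at 3 h. That is the natural reading of the two consecutive sentences, but the text does not say so expressly. Maximum dose per kg = rate × minutes.

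- Section 7.1 read literally: 80 × 720 = 57,600 ng/kg = 57.6 µg/kg.
- Section 7.1.6: 80 × 180 + 40 × 540 = 14,400 + 21,600 = 36,000 ng/kg = 36.0 µg/kg.
- Difference: 57.6 − 36.0 = 21.6 µg/kg. Ratio: 57.6 / 36.0 = 1.6.

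The protocol states no cumulative dose to compare these with. They are upper limits, and no body weight needs to be assumed.

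**Step 4: size of the goal discrepancy.** It cannot be computed, because the protocol puts no number on a low level of norepinephrine.

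**Step 5: does the same clinician have to run both arms?** Sections 4 and 7.1.10 suggest so. Sections 5.1 and 8.3 name different people, and neither says who adjusts the rate or whether that person is blinded. If the titrating staff are blinded, they cannot apply arm-specific goals. If they are not, the arms are openly titrated to different goals. The two goals for the angiotensin II arm conflict in either case.

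**The case against.** The strongest reply is that section 7.1 is a short summary giving the absolute maximum, which is also the maximum in 7.1.6, and that 7.1.6 merely adds the timing. **This largely stands.** A reader might infer that the protocol authorises twice the maintenance limit for 9 of the 12 hours. To act on that, staff would have to disregard sections 7.1.6, 7.1.7 and 8.1 and the instruction to use the lowest compatible dose. What remains is an unqualified limit that should be corrected to match.

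A second reply is that both versions of the goal have angiotensin II displacing norepinephrine, so the treatment concept is the same. **This stands in part.** A reader might infer that the protocol leaves open whether angiotensin II simply sits on top of unchanged norepinephrine. It does not: a MAP target without weaning appears only in the control text. Stopping norepinephrine and leaving a low dose running are nevertheless different instructions.

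Third, saline cannot displace norepinephrine, so a weaning goal would change little for controls, and the synopsis already supplies the norepinephrine adjustment missing from the placebo text of 7.1.6. **This stands as to effect.** The case for common wording rests on blinded staff needing one instruction. It is weakened, though not removed, by the protocol's silence on who titrates.

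Finally, a reader might infer consequences for the per-protocol analysis. Which deviations exclude a patient is commonly left to the statistical analysis plan, which is not at hand, and missing a titration goal is nowhere called a violation. That inference is not supported.

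**Conclusion.** The protocol is wrong as written on two counts.

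- **Main point.** The norepinephrine goal for the angiotensin II arm is contradictory: complete weaning in the synopsis and section 7.1, consistent with section 2.2, against an unquantified low level in the operative section 7.1.6. The control text carries no matching instruction. The effect on the vasopressor-dose endpoint is plausible but cannot be quantified.
- **Secondary point.** Section 7.1 omits the time limit on the 80 ng/kg/min ceiling. Read literally, it permits at most 57.6 against 36.0 µg/kg over 12 h, a ratio of 1.6, assuming maintenance starts at 3 h. This is a permitted maximum rather than an expected dose, and the protocol's own cross-references indicate that the lower limit governs.

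A reader might go on to infer a bias in the biomarker comparison. The document gives no basis for one in either direction, and none is claimed. The point should be corrected because it concerns the treatment rule and a safety limit, and the correction is simple.

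**What to change.** 1. **Section 7.1.6, Daily dose:** replace the low-level goal with complete weaning of norepinephrine as far as MAP above 65 mmHg and the dose cap allow. Norepinephrine is kept or restarted if MAP is not held at the cap. The synopsis and sections 7.1 and 2.2 point to this choice; the sponsor's clinicians should confirm it.
2. **Both arms:** give the same norepinephrine instruction for the study drug, whichever syringe the patient receives, in section 7.1.6 and in the synopsis.
3. **Section 7.1:** replace the bare 80 ng/kg/min ceiling with up to 80 ng/kg/min in the first 3 h and 40 ng/kg/min thereafter.
4. **Section 7.1.6, Control/Placebo:** adopt the synopsis rule that the control substance and norepinephrine are both adjusted to MAP above 65 mmHg.

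The cost is a few sentences. Blinding, sample size, drug handling and data collection do not change. The one downside is that some angiotensin II patients will remain on norepinephrine at the cap, so complete weaning becomes a goal rather than a requirement.
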